A sample size of 33 people per group was determined. The study supervisor oversaw the use of a basic randomization program to carry out the random allocation. The Sequentially Numbered, Opaque, Sealed Envelope (SNOSE) technique was used to guarantee allocation concealment. Outcome assessors were subjected to single blinding; they were not told about group allocations and were not allowed to look for relevant information. The "SI Kumbang" and "Bugar Lansia" gymnastics exercise regimens were part of the intervention groups. For 12 weeks in a row, both therapies included three 30-minute sessions per week. Participants received adaption sessions to acquaint themselves with the workout regimens throughout the first week. The Borg Scale was utilized to track intensity.

The Six-Minute Walk Distance (6MWD) for cardiorespiratory endurance, and handgrip strength muscle measured using a handgrip JAMAR. The Physical Activity using Physical Activity Scale for the Elderly (PASE) questionnaire, the balance using Short Physical Performance Battery (SPPB) were among the outcome measures and the immunity aspect using inflammasome marker Caspase-1 and IL-18. The research team reviewed patient logbooks at the beginning of each week to track adverse effects such weariness, shortness of breath, pain, or dizziness. At RS Islam Jakarta Pondok Kopi, every suspected adverse event was swiftly assessed, and any required medical attention was given. Every adverse event was reported to the ethics committee of the institution.

Data analysis was performed using SPSS 29.0 tests with significance set at  $p<0.05$ . Descriptive summaries of the sample characteristics were provided. Prior to analysis, the normality of the data was checked. Dependent t-tests were used to compare pre intervention and post intervention score in the SI Kumbang and Bugar Lansia groups for normally distributed outcomes (6MWD, handgrip, SPPB, PASE, Caspase-1, IL-18); the Wilcoxon test was used to assess non-normal data. Independent t test or Mann-Whitney U test is used for compared the effectiveness of the two interventions ( $\Delta$  score). A p-value of less than 0.05 was deemed significant.

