Baseline characteristics of clinical outcomes of physical performance and immunity in elderly prior to intervention. Both groups are similar except for IL-18, which will be adjusted using ANCOVA analysis.

Table 2. Baseline Characteristics of Physical Performance and Immunity in Elderly before Intervention

| Variabel   | Si Kumbang
(n=33) | Bugar Lansia
(n=33) |
|---|------------------------------|--------------------------------|
| The Six-Minute Walk Test (6MWT) (meters), median (IR)              | 344,75 (293,75 – 376,5)      | 353 (311,25 – 375,75)          |
| Handgrip strength (kg), mean (SD)                                  | 16,11 (3,30)                 | 16 (3,39)                      |
| Skor The Short Physical Performance Battery (SPPB), median (RIK)   | 9 (9 – 11)                   | 9 (8,25 – 10,75)               |
| Skor The Physical Activity Scale for the Elderly (PASE), mean (SD) | 19,31 (2,73)                 | 20,67 (3,97)                   |
| CASPASE-1, mean (SD)   | 52251,52 (26750,02)          | 56129 (25767,23)               |
| IL-18, median (IR)   | 186,77 (136,37 – 295,03)     | 279,56 (190,67 – 438,45)       |

IR (interquartile range); SD (standard deviation)

The impact of the SI Kumbang group and Bugar Lansia group gymnastic exercise interventions on physical performance and immunity are displayed in Table 3. SI Kumbang group had significantly impact in cardiorespiration endurance (6MWD) ( $p=0.005$ ) and physical activity (PASE) ( $p = 0.001$ ). However, there was no significant impact on strength muscle (handgrip JAMAR) ( $p=0,136$ ), and balance (SPBB) ( $p=0,194$ ). Immunity in elderly showed, both group there were no significant in inflamasome Caspase-1 ( $p=0,055$ ) and IL-18 ( $p=0,327$ ). For IL-18, adjustment was performed using the ANCOVA test ( $p=0.255$ ).

Table 3. Impact Of “SI Kumbang” Exercise and “Bugar Lansia” on Physical Performance and In Elderly Analysis

| Variables                            | “SI Kumbang”
group (n=33) | “Bugar Lansia”
group (n=33) | p           | Adjusted |
|---|--------------------------------------|--|--------------------|-----------------|
|   | $\Delta$                             | $\Delta$                               |                    |                 |

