## DISCUSSION

This study is the first to test the new SI Kumbang gymnastics exercise. Randomization has been performed, and the baseline demographic and clinical characteristics of the two groups are not different, except for IL-18, which shows a difference and is adjusted using ANCOVA.

From the clinical baseline data, the clinical picture of 6MWD, balance, and physical activity is less than normal. This illustrates the condition of elderly people who are generally inactive or sedentary in Indonesian society, that these three physical performances have indeed declined in elderly people entering the age of 60-70 years. In general, they will experience a decline in physical condition and health, especially in healthy elderly people who are inactive in sports, sedentary, or with various chronic diseases.

Other studies analyzed the relationship between sedentary time and physical endurance in elderly. They compared 83 older adults aged 60-87 years. Physical activity (light, moderate, or vigorous) and sedentary time were assessed using ActiGraph® GT1M Accelerometers (Fort Walton Beach, FL, USA). The Senior

Fitness Test assesses five physical fitness components (aerobic endurance, muscular strength, agility/dynamic balance, flexibility, and BMI), and includes six tests: 6-min walk distance (meters); chair stand test (repetitions/30 s); arm curl test (repetitions/30 s); 2.44 m up and go test (seconds); chair sit and reach test (centimeters); and back scratch test (centimeters). Regarding physical endurance, when compared to the inactive group, the active group achieved higher average results on aerobic endurance (6 min walk distance), upper and lower limb strength (arm curl and chair stand test, respectively), agility/dynamic balance. Elderly people are more likely to experience frailty, which many of us mistakenly believe to be a natural aspect of aging. It might be challenging to diagnose frailty in daily life and to differentiate between frailty syndromes and the normalcy associated with age vulnerabilities.

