active and inactive elderly individuals. The significant difference in PASE scores between the SI Kumbang exercise group and the control group in this study likely reflects the interaction between environmental, social, and daily behavioral factors that influence increased physical activity among the elderly outside of exercise activities. The increase in the average PASE score in the SI Kumbang exercise group shows a promising trend that could lead to a significant increase in physical activity levels and better functional health outcomes.

The decrease in Caspase-1 levels in both groups indicates that the exercise intervention successfully reduced inflammatory activity in older adults associated with inflammasomes. These results are in line with a systematic review by Bautmans et al., which found that various types of exercise, especially those combining resistance and aerobic components, can reduce Caspase-1 and other proinflammatory cytokines such as IL-1 $\beta$ , IL-6, and IL-18, thereby altering the inflammatory profile of older adults. The downregulation of inflammasome signaling pathways is demonstrated by the reduction in Caspase-1, a crucial enzyme that activates cytokines from the IL-18 family. Although there were no differences in changes between the two exercise groups.

Following exercise intervention, IL-18 levels did not decrease because the analysis of the process pathway showed that caspase-1 activation requires various processes to produce a decrease in IL-18, that activated caspase-1 will cleave the same tetrapeptide site in pro-IL-18. The crystal structure of the caspase-1 and pro-IL-18 complex reveals a two-site (binary) substrate recognition mechanism, a catalytic pocket that binds the tetrapeptide, and a unique exosome that critically recognizes GSDMD10 and binds to a specific structure formed jointly by the propeptide sequence and the post-cleavage site in pro-IL-18. This binary recognition is also used by caspase-1 to process pro-IL-18; structural deviations around the exosite underlie its inability to target rationally designed pro-IL-18. The structure of pro-IL-18 displays an autoinhibitory interaction between the propeptide and the post-cleavage site region, preventing recognition by the IL-18R $\alpha$  receptor.

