## CONCLUSION

Both SI Kumbang and Bugar Lansia gymnastic exercises improved physical performance in older adults, as shown by significant gains in cardiorespiration endurance and physical activity in elderly. And there is no difference in physical performance aspects such as muscle strength, balance, and immunity aspects as Caspase-1 and IL-18 in the elderly.

These study results indicate that although both exercise modalities are effective in enhancing physical performance in elderly, SI Kumbang appears to provide superior benefits, particularly in improving cardiorespiration endurance and physical activity in elderly.

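### Arms are compared on unadjusted change scores, with baseline adjustment only for IL-18 because its baseline looked different; the Caspase-1 no-difference verdict may depend on that choice

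*Combined protocol and SAP*

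**What the plan says.** The data-analysis paragraph of METHODS gives one approach for comparing the arms, applied to the change score: "Independent t test or Mann-Whitney U test is used for compared the effectiveness of the two interventions". The threshold is stated as "A p-value of less than 0.05 was deemed significant". ANCOVA does not appear in that section.

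It first appears in RESULT, above Table 2: "Both groups are similar except for IL-18, which will be adjusted using ANCOVA analysis". The DISCUSSION gives the same reason: "except for IL-18, which shows a difference and is adjusted using ANCOVA". Table 3 accordingly has an adjusted p-value for IL-18 only (0.255, against 0.327 unadjusted). The other five outcomes have none.

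For Caspase-1, Table 3 reports p=0.055 from the independent t test. The DISCUSSION reads this as "Although there were no differences in changes between the two exercise groups", and the CONCLUSION says "there is no difference in physical performance aspects such as muscle strength, balance, and immunity aspects as Caspase-1 and IL-18".

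**The concern.** Whether baseline adjustment is worthwhile depends on how strongly baseline predicts the final value. Choosing the covariate after inspecting the baselines, for one outcome out of six, is not a sound substitute for a stated rule. It also leaves PASE unadjusted although its arms differ by 0.40 SD at baseline.

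A change-score comparison is unbiased over repeated randomisations. However, it fixes the slope of the final value on baseline at 1. When the true slope is not 1 it loses precision, and given the imbalance actually observed it is biased.

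The Caspase-1 verdict sits just above 0.05, so it could be the product of an inefficient test. The size of the PASE effect could be off as well. For IL-18, the one adjusted outcome, no transformation is described, although it is summarised by medians and its change is tested by Mann-Whitney.

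**Working it through.** **Inputs.** Two-sided 5% level (sidedness is not stated) and 33 per arm: "A sample size of 33 people per group was determined". Baseline means and SDs come from Table 2 and change means and SDs from Table 3, SI Kumbang first.

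- Caspase-1: baseline 52,251.52 (26,750.02) and 56,129 (25,767.23); change -38,945.33 (27,628.63) and -24,957.94 (30,423.15).
- PASE: baseline 19.31 (2.73) and 20.67 (3.97); change 5.39 (4.38) and 1.16 (5.26).

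**Step 1: reproduce the printed result.** The Caspase-1 change difference is -38,945.33 + 24,957.94 = -13,987. Its SE is √[(27,628.63² + 30,423.15²)/33] = 7,154. With 64 df, t = -1.955, p = 0.0549 and the 95% CI is -28,279 to 304. This matches the printed 0.055.

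**Step 2: baseline gaps.** Caspase-1: 52,251.52 - 56,129 = -3,877, or -0.15 SD. PASE: 19.31 - 20.67 = -1.36; the pooled SD is √[(2.73² + 3.97²)/2] = 3.41, giving -0.40 SD (t-test p=0.11).

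**Step 3: rebuild ANCOVA.** Post-intervention SDs are not printed, so they are varied. In each arm the baseline-to-post correlation is

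r = (SD_base² + SD_post² - SD_change²) / (2 × SD_base × SD_post).

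The pooled within-arm slope is b = Σ(r × SD_base × SD_post) / Σ(SD_base²), summed over arms. The adjusted difference is the change difference + (1 - b) × the baseline difference. Its SE is √{(RSS/63) × [2/33 + (baseline difference)²/Sxx]}, where Sxx = 32 × Σ(SD_base²), RSS = 32 × [Σ(SD_post²) - b² × Σ(SD_base²)], and there are 63 df.

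Example, Caspase-1 with post SDs equal to baseline SDs: r = 0.467 and 0.303, so b = 0.388. The adjusted difference is -13,987 + 0.612 × (-3,877) = -16,361, with SE 6,023 and p = 0.0085.

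The last two columns repeat the calculation for a baseline gap of zero and a reversed gap, in case Table 2 does not describe the participants analysed.

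| Post SD (both arms) | Slope b | Adjusted difference (95% CI), printed gap | p, printed gap | p, zero gap | p, gap reversed (+3,877) |
|---|---|---|---|---|---|
| baseline SDs | 0.39 | -16,361 (-28,398 to -4,324) | 0.0085 | 0.023 | 0.058 |
| 30,000 | 0.54 | -15,770 (-28,913 to -2,627) | 0.0195 | 0.037 | 0.068 |
| 35,000 | 0.78 | -14,857 (-29,006 to -707) | 0.040 | 0.052 | 0.069 |
| 40,000 | 1.05 | -13,802 (-28,239 to 634) | 0.061 | 0.057 | 0.054 |

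With the printed gap and both post SDs scaled together, p exceeds 0.05 only between about 1.42 and 1.90 times the baseline SDs, with a maximum of 0.070.

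**Step 4: the same question by correlation.** Regressing change on arm and baseline, with the baseline-to-change correlation set equal in both arms, gives p = 0.070 at +0.3, 0.058 at 0, 0.031 at -0.3 and 0.012 at -0.5. The result crosses 0.05 at about -0.09. The implied SI Kumbang post mean is 52,252 - 38,945 = 13,306. A zero correlation would need a post SD near 38,457 around that mean, which is hard to credit for a marker that cannot be negative. A negative correlation is therefore plausible.

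**Step 5: other outcomes.**

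- PASE: 4.23 unadjusted. Adjusted: 2.86 at baseline-level post SDs, 3.64 at 5, 3.95 at 5.5, 4.29 at 6 and 4.65 at 6.5, with p between 0.0002 and 0.003.
- Handgrip: p from 0.064 to 0.14 for post SDs of 2.5 to 4.
- 6MWD, SPPB and IL-18 are printed as medians and cannot be rebuilt.
- IL-18 baseline skew, as (Q3 - median)/(median - Q1): 2.15 and 1.79 on the raw scale, 1.45 and 1.18 after taking logs.

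**Step 6: participant counts.** Table 1 shows 36 women per arm under headings of n=33. The Table 3 means and SDs give Caspase-1 p=0.0549 at 33 per arm but 0.0449 at 36. For handgrip they give 0.138 at 33 and 0.121 at 36, against a printed 0.136. Table 3 therefore fits 33. If age and PASE are recorded as whole numbers (an assumption), the SI Kumbang means of 65.25 and 19.31 are possible with 36 people (2,349/36; 695/36) but not with 33. Baseline and change figures may describe different people.

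**The case against.** The strongest reply is that the Caspase-1 consequence is unproven. It needs post-intervention SDs or a correlation that the document does not print, and the scenarios fall on both sides of 0.05. They also combine Table 2 SDs with Table 3 change SDs when the two tables may not cover the same participants, and the baseline SDs themselves were not varied. All of this stands, and the computed p-values should not be read as results.

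The grid is not a firm bound either. With post SDs equal to the implied post means (13,306 and 31,171), p is 0.004, and at 20,000 in both arms it is 0.0007. In the 13,306/31,171 case, however, the arm slopes are 0.09 and 0.53 (interaction p=0.04), so a common slope on the raw scale is itself doubtful.

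It can also be said that change scores are valid in a randomised trial, and that replacing the stated test once p=0.055 is known invites selection. The first point is right: this is a loss of efficiency and an unsound selection rule, not an invalid test. The second is met by adjusting every outcome, labelling the work post hoc and keeping the stated tests in view.

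The participant counts, multiplicity and the reading of p=0.055 as equality are separate faults, though each affects how the Caspase-1 result can be reported. Silence about an IL-18 transformation in a short report does not prove that none was used.

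**Conclusion.** The concern holds. Two parts are definite. Adjustment was given to one outcome because its baseline looked different, with no mention in METHODS. And the no-difference statement for Caspase-1 is unsupported even without adjustment, because the interval of -28,279 to 304 includes large differences.

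The third part is conditional. With 33 per arm, Table 2 SDs that apply to those 33 and the printed imbalance, ANCOVA gives p between 0.0085 and 0.061 for post SDs from baseline level to 40,000. A zero or reversed imbalance moves several of these above 0.05. The verdict may change but need not.

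The PASE estimate could shrink from 4.23 to 2.86 or rise slightly; its significance is not in doubt. Handgrip stays non-significant over the range tried. This should be fixed; confidence is medium because only the trial data can settle the adjusted values.

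**What to change.** 1. Reconcile the 33 and 36 counts, and use the same participants for baseline and change.
2. For every outcome, whatever its imbalance, fit ANCOVA of the week-12 value on arm and that outcome's own baseline. Report the adjusted difference, 95% CI and p-value. Use a log scale for IL-18, and for Caspase-1 if residuals are skewed. Check the common-slope assumption. Use a rank or ordinal model with baseline for SPPB.
3. Drop the rule that adjusts only where baselines differ, and keep the change-score tests as sensitivity analyses.
4. Label the re-analysis post hoc.
5. Replace the Caspase-1 no-difference wording with the adjusted estimate and its interval. Claim no Caspase-1 benefit without stating that six outcomes are tested at 0.05 with no multiplicity control. The Bonferroni threshold is 0.05/6 = 0.0083, which the 0.0085 scenario misses and the 0.004 scenario meets.

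The cost is a check of participant counts, a few SPSS runs on data already held, and rewording. The reported PASE difference may become smaller.

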### Abstract

**Background:** The most common issue associated with aging is frailty, which has a significant impact on the physical performance and immunity of older adults. Exercise is the primary modality in medical rehabilitation. The Indonesian Strong and Balanced Healthy Exercise (SI Kumbang) gymnastic exercise is a newly designed exercise model developed by researchers, which is a type of low-impact aerobic exercise with moderate intensity. SI Kumbang exercises are performed three times a week for 30 minutes over a period of 12 weeks. The main basis of these exercises is foot movements that follow a rhythm, with the feet rotating in sequence in the four cardinal directions.

**Objective:** This study aimed to evaluate and compare the impact of SI Kumbang gymnastic exercises and Bugar Lansia gymnastic exercise programs on physical performance and immunity in elderly.

**Methods:** A randomized single-blind clinical trial involved 66 elderly participants aged 60–70 years, divided into SI Kumbang (n=33) and Bugar Lansia (n=33) groups. Each group exercised three times weekly for 12 weeks. Outcomes measured for physical performance were cardiorespiration endurance using Six-Minute Walk Distance (6MWD), strength muscle using handgrip JAMAR, balance using Short Physical Performance Battery (SPPB), physical activity using Physical Activity Scale for the Elderly (PASE). Outcomes measured for immunity were inflamasome using Caspase-1 and IL-18. Data were analyzed using SPSS 29.0 tests with significance set at  $p<0.05$ .

**Results:** Physical performance in elderly showed, SI Kumbang group had significantly impact in cardiorespiration endurance (6MWD) ( $p=0.005$ ) and physical activity (PASE) ( $p=0.001$ ). However, there was no significant impact on strength muscle (handgrip JAMAR), and balance (SPBB). Immunity in elderly

showed, both group there were no significant in inflamasome Caspase-1 ( $p=0,055$ ) and IL-18 ( $p=0,255$ ).

**Conclusion:** In conclusion, SI Kumbang gymnastic exercise group has more significant impact in terms of physical performance, particularly in enhancing cardiorespiration endurance and physical activity rather than Bugar Lansia gymnastic exercise group. And there is no difference in physical performance aspects such as muscle strength, balance, and immunity aspects as Caspase-1 and IL-18 in the elderly.

**Keywords:** elderly, physical performance, immunity, SI Kumbang exercise gymnastics.

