## METHODS

This study was designed as a randomized clinical trial with allocation concealment and single blinding to assess how the "SI Kumbang" gymnastic exercise and the "Bugar Lansia" gymnastic exercise model affected physical performance and immunity in elderly. In cooperation with the Rehabilitation Medicine Polyclinics, the 12-week intervention took place at the Ahmad Dahlan Indoor Hall of RS Islam Jakarta Pondok Kopi, East Jakarta, between April until September 2025. According to the FI-40 score, the target demographic was made up of senior citizens who were categorized as robust and pre-frail. Patients who visited the Rehabilitation Medicine Polyclinics at RS Islam Jakarta Pondok Kopi during the study period were included in the accessible population.

Female participants between the ages of 60 and 70 who met the following inclusion criteria were categorized as pre-frail (FI-40 score  $> 0.08 < 0.25$ ) or robust (FI-40 score  $\leq 0.08$ ) and had a body mass index (BMI) between 18.5 and 24.9. Participants had to have managed diabetes mellitus (GDS  $\leq 120$  mg/dL) and blood pressure ( $\leq 130/80$  mmHg) without taking any drugs that affected heart rate. Only those who were willing to participate, able to adhere to the study procedures, and had not been enrolled in any organized exercise program in the previous three months were included. Chronic heart or lung conditions, chronic conditions that cannot be reversed (e.g., cancer or chronic renal disease), diabetes complications in the extremities, motor impairment (MMT  $< 5$ ), knee pain, lower limb deformities

(genu varus/valgus), and hand deformities were among the exclusion criteria. Dropouts were defined as those who did not finish the study, missed more than six workouts, or had negative outcomes linked to the intervention.

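### The between-arm tests treat the 33 women per arm as independent although sessions were very likely shared; a class-aware sensitivity analysis should precede any general superiority claim, above all for 6MWD.

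*Combined protocol and SAP*

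**What the plan says.** **Allocation.** Women appear to have been randomised individually. METHODS says "The study supervisor oversaw the use of a basic randomization program to carry out the random allocation", with sequentially numbered sealed envelopes. "A sample size of 33 people per group was determined", with no stated allowance for clustering.

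**Delivery.** METHODS states that "the 12-week intervention took place at the Ahmad Dahlan Indoor Hall of RS Islam Jakarta Pondok Kopi", and gives both programmes three 30-minute sessions a week for 12 weeks. Nothing is said about class size, number of classes per arm, instructors or intakes.

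**Analysis.** For the comparison between arms, "Independent t test or Mann-Whitney U test is used for compared the effectiveness of the two interventions", applied to change scores, and "A p-value of less than 0.05 was deemed significant". The only adjustment reported anywhere is the ANCOVA for IL-18, made because of its baseline difference. No analysis has a term for class, session, instructor or intake.

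**Conclusion.** The CONCLUSION section says that "SI Kumbang appears to provide superior benefits, particularly in improving cardiorespiration endurance and physical activity in elderly". This rests on 6MWD (p=0.005) and PASE (p=0.001) in Table 3.

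**The concern.** When participants are randomised one by one but treated in groups, the treatment itself can make outcomes alike within a group, for example through common pacing or company. An independent t test or Mann-Whitney U test ignores this. If the correlation is positive, the standard error is too small for a statement about the programme beyond the particular classes that received it.

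Two positive tests out of six carry the superiority claim, so it matters whether they would survive a reasonable allowance. If each arm trained as a single class, there is a harder limit: a good class and a good programme cannot be told apart by any analysis.

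**Working it through.** **1. Are the printed p-values unadjusted tests on 66 women?** Independent t tests from the Table 3 means and SDs, with n=33 per arm:

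- PASE: difference 5.39 − 1.16 = 4.23; SE = √(4.38²/33 + 5.26²/33) = 1.19; t = 3.55, p = 0.0007 (printed 0.001).
- Handgrip: t = −1.50, p = 0.138 (printed 0.136).
- Caspase-1: t = −1.96, p = 0.055 (printed 0.055).

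So they are. The 6MWD Mann-Whitney p needs the raw ranks and cannot be reproduced. A rough t test from its medians and quartiles (mean taken as the average of the three, SD as interquartile range/1.35) gives p = 0.0017, the same order as 0.005.

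**2. How likely are shared sessions?** Seeing 66 women singly in one intake would take 66 × 3 × 0.5 h = 99 hall-hours a week; two equal intakes would still take 49.5. Shared sessions are a strong inference, but an inference.

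**3. Size, on assumed values.** The documents give neither ICC nor class size. I take ICC 0 to 0.10 and one, two or three equal classes per arm (m = 33, 16.5, 11).

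- Design effect: DE = 1 + (m − 1) × ICC.
- Actual two-sided error of the nominal 5% test: 2 × [1 − Φ(1.96/√DE)].
- Allowed-for p: 2 × [1 − Φ(z/√DE)], with z taken from the printed p: 2.81 for 6MWD, 3.29 for PASE.

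| Classes per arm | ICC | DE | Actual error | 6MWD p | PASE p |
|---|---|---|---|---|---|
| any | 0 | 1.00 | 5.0% | 0.005 | 0.001 |
| 3 (m=11) | 0.01 | 1.10 | 6.2% | 0.007 | 0.002 |
| 3 | 0.05 | 1.50 | 11.0% | 0.022 | 0.007 |
| 3 | 0.10 | 2.00 | 16.6% | 0.047 | 0.020 |
| 2 (m=16.5) | 0.01 | 1.16 | 6.8% | 0.009 | 0.002 |
| 2 | 0.05 | 1.77 | 14.1% | 0.035 | 0.014 |
| 2 | 0.10 | 2.55 | 22.0% | 0.079 | 0.039 |
| 1 (m=33) | 0.01 | 1.32 | 8.8% | 0.015 | 0.004 |
| 1 | 0.05 | 2.60 | 22.4% | 0.082 | 0.041 |
| 1 | 0.10 | 4.20 | 33.9% | 0.171 | 0.108 |

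Simulated Mann-Whitney tests (20,000 runs per setting) agree at ICC 0.01, 0.05 and 0.10: 8.5%, 21.9% and 34.7% with one class per arm; 6.3%, 10.6% and 16.2% with three.

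**4. Break-even.** p reaches 0.05 when DE = (z/1.96)².

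- 6MWD: DE = 2.05, so ICC = 1.05/(m − 1) = 0.033 with one class per arm, 0.068 with two (1.051/15.5 before rounding) and 0.105 with three.
- PASE: DE = 2.82, so ICC = 0.057, 0.117 and 0.182.

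**5. Degrees of freedom are a separate matter.** Three classes per arm leave 2 × 3 − 2 = 4 df for a class-level test (critical t 2.776). A statistic of 2.81 on 4 df gives p = 0.048 even at ICC 0. At ICC 0.05 it becomes 2.81/√1.5 = 2.29, p = 0.084 on 4 df against 0.022 on a normal reference. Most of that shift is lost df, not clustering.

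**The case against.** **The premise is inferred.** No text mentions a class, a leader or a timetable. In the Abstract, "Each group exercised three times weekly for 12 weeks" uses the word for the trial arm, so it is no evidence of joint sessions. Rhythm and music are described for SI Kumbang, not for Bugar Lansia, so a common beat cannot be assumed in both arms. This stands. Shared sessions remain very likely on hall time, but shared sessions do not by themselves prove correlated outcomes, and an ICC of zero belongs in the range.

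**The large figures need one class per arm.** Recruitment of clinic attendees during the study period, and an April to September window for a 12-week programme, leave room for staggered intakes and smaller classes. This also stands. A reader might infer that the true error is well above 5%, or that the 6MWD finding is lost. The documents support neither: in the table above, 6MWD passes 0.05 in three rows and PASE in one.

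**The inflation depends on the question.** Under individual randomisation, a test of no difference between the two programmes as delivered, in these classes, keeps its nominal level. The excess arises when the result is generalised to other classes. This is right, and it fixes the scope of the point. But the CONCLUSION section does generalise, since it speaks of the two exercise modalities in elderly people.

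**A mixed model may be barely estimable.** With two or three classes per arm the class variance is poorly estimated, and with one it is not estimable. That argues against replacing the planned test, but not against a sensitivity analysis beside it.

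**Conclusion.** The point holds in conditional form. The analysis makes no allowance for shared sessions, and the printed p-values are confirmed as tests on 66 independent women. If change scores are positively correlated within classes, those p-values are too small for a claim about the programmes in general.

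The size rests wholly on assumed class structure and ICC. The excess over 5% may be nil, small with several classes and low ICC, or large with one class per arm. On a normal reference 6MWD survives most of the range considered and fails only above a design effect of about 2.05. PASE fails only above about 2.82.

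What is established is that the documents omit the facts needed to judge this, and that the superiority wording is broader than the analysis supports until they are given.

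**What to change.** 1. In METHODS, state the number and size of classes, the instructors and the intakes in each arm.
2. Keep the independent t test or Mann-Whitney U test and add a sensitivity analysis for 6MWD and PASE.
   - With more than one class per arm: a mixed model of the change score (rank-transformed where non-normal) with arm fixed and class random, or a class-level analysis, in either case with small-sample degrees of freedom.
   - With one class per arm, or if class membership was not recorded: p-values and confidence intervals widened by a design effect at ICC 0, 0.01, 0.05 and 0.10.
3. Unless the result holds in that analysis, limit the superiority wording in the Abstract and CONCLUSION to the classes studied. With one class per arm, say also that programme and class effects cannot be separated.

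This needs no new participants or measurements. The mixed model depends on class membership having been recorded. The rule on more than six missed workouts implies that attendance was tracked, but the documents do not describe such records. The downside is wider intervals and possibly a weaker 6MWD claim.
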